PROTOCOL AND STATISTICAL ANALYSIS PLAN

Protocol Title: Assessing the Efficacy of Digital Health Technology in the Management of Congestive Heart Failure: An Evaluation of Three Novel Digital Health Products

NCT: NCT04394754

HRP-503B – BIOMEDICAL RESEARCH PROTOCOL (2017-1)

Protocol Title: Assessing the Efficacy of Digital Health Technology in the Management of Congestive Heart Failure: An Evaluation of Three Novel Digital Health Products

Principal Investigator(s): F. [name] MSCE, [name] MD MPH, [name] MD MPH Co-Investigators: TBD

Version Date: February 16th, 2021

Clinicaltrials.gov Registration #: NCT04394754

INSTRUCTIONS

This template is intended to help investigators prepare a protocol that includes all of the necessary information needed by the IRB to determine whether a study meets approval criteria. **Read the following instructions before proceeding:**

- 1. Use this protocol template for a PI initiated study that includes direct interactions with research subjects. Additional templates for other types of research protocols are available in the system Library.
- 2. If a section or question does not apply to your research study, type "Not Applicable" underneath.
- 3. Once completed, upload your protocol in the "Basic Information" screen in IRES IRB system.

SECTION I: RESEARCH PLAN

1. **Statement of Purpose:** State the scientific aim(s) of the study, or the hypotheses to be tested. The purpose of this study is to determine the efficacy of three novel digital health technologies versus usual care in the management of congestive heart failure, as assessed by a primary outcome of improvement in quality of life, and a variety of secondary outcomes that include metrics measuring patient and provider satisfaction, clinical efficiency, and patient outcomes.

2. Probable Duration of Project:

We anticipate the duration of the study to be 12 months. Three months will be spent developing all studyrelated materials including protocols, consents and recruitment materials, and completing training of site coordinators and providers. Eight months will be spent recruiting patients and performing follow up visits. The last month will be spent performing data analysis activities.

3. **Background:** Describe the background information that led to the plan for this project. Provide references to support the expectation of obtaining useful scientific data.

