The study was designed to provide adequate power to detect a clinically significant change in the primary outcome measure, the score on the Kansas City Cardiomyopathy Questionnaire.⁸

The 23-item questionnaire has been validated in multiple heart failure populations, and quantified the physical limitations, symptoms, self-efficacy, social interference, and quality of life associated with living with heart failure. The KCCQ composite score can theoretically range from 0 - 100 (with 100 being the best possible score) and a change of 10 points has been determined to be the minimum clinically important difference. Within a given patient, the score is quite stable in the absence of clinical changes, with a within-patient standard of deviation of 11.8 for patients with no change in clinical status.⁹

In order to detect the minimum clinically important difference of a 10-point improvement in the KCCQ, we would need to enroll 40 patients in each arm of the trial across all centers to provide 90% power at an alpha threshold of 0.017. This gives a total of enrollment of 160. Given uncertainties around the intraclass correlation coefficient (assumed to be 0.10 here and reflecting the overall efficacy of each individual clinic) we will inflate the target sample size to 200, or 50 per arm of the trial. The lower alpha threshold represents a bonferonni correction that provides statistical power to test multiple comparisons – each of the 3 digital health interventions against the control intervention. We will attempt to balance recruitment across the centers with a per-center target of 5 individuals per trial arm.

An interim analysis will be completed at 50% enrollment. We will stop the trial for efficacy for a p value threshold of < 0.0006. Given the interim analysis, the threshold p-value for statistical significance at the end of the trial will be 0.016.

The primary analysis will be a mixed effects model comparing change in KCCQ over time in the intervention group versus the control, without accounting for a center-by-treatment interaction. In secondary analyses, we will model that interaction to determine if certain interventions are uniquely effective in certain centers.

Secondary and exploratory analyses will examine the outcomes listed above using the same procedure applied to baseline variables for outcomes assessed at one time point, and using mixed-effects models for continuous outcomes assessed at multiple timepoints.

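### Optional improvement, not an error: Holm steps (0.016, 0.024, 0.048) at the final analysis would recover some power for a second or third effective product at the same family-wise limit

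*Combined protocol and SAP*

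**What the plan says.** All the testing rules are in Section I, item 13 (Statistical Considerations).

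- The sample size is set "to provide 90% power at an alpha threshold of 0.017". The plan explains that "The lower alpha threshold represents a bonferonni correction that provides statistical power to test multiple comparisons", namely "each of the 3 digital health interventions against the control intervention".
- On the interim: "An interim analysis will be completed at 50% enrollment", and "We will stop the trial for efficacy for a p value threshold of < 0.0006".
- After that look, "the threshold p-value for statistical significance at the end of the trial will be 0.016".
- The standard deviation offered for the KCCQ score comes "with a within-patient standard of deviation of 11.8 for patients with no change in clinical status".

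The overall level and the sidedness of the tests are not stated. Nothing in the document raises the final threshold for the remaining devices once one has succeeded. Nor does it say whether one device crossing 0.0006 ends the whole trial or only that comparison. Section I, item 1 (Statement of Purpose) gives the aim as "to determine the efficacy of three novel digital health technologies versus usual care in the management of congestive heart failure", so a verdict on each product is part of the purpose.

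**The concern.** A single-step Bonferroni rule holds every comparison to the same threshold whatever the other two show. Once one device has been declared effective, at most two null hypotheses can still be true, yet the plan tests them as if there were three. With two true nulls its error bound is 2 x 0.0166 = 0.0332, and with one it is 0.0166. The rest of the 0.05 is left unused.

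At stake is power for a second or third effective product, in a trial set up to judge three. The chance of finding at least one effective product when all three work is not at stake, and neither is the validity of the current rule.

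**Working it through.** **Inputs from item 13.** Three comparisons with a shared control; planning alpha 0.017; interim 0.0006 at 50% enrollment; final 0.016; effect 10 points; SD 11.8; 40 per arm before inflation and 50 after.

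**Assumptions.** Family-wise 0.05, two-sided tests, both thresholds applied to each comparison, and half the information available at the interim. A second SD of 11.8 x √2 = 16.7 is shown because the 11.8 is a within-patient figure while the analysis is of change. The documents do not give 16.7.

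**Reproducing the plan's figures.**

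- 0.05/3 = 0.0167, which rounds to the stated 0.017. Then 0.0167 − 0.0006 = 0.0161, stated as 0.016.
- Family-wise bound: 3 x (0.0006 + 0.016) = 0.0498.
- Sample size: n = 2 x 11.8² x (2.387 + 1.282)² / 10² = 37.5, so 38 per arm two-sided (39 with the t distribution), close to the stated 40. One-sided gives 33. Two-sided testing at SD 11.8 is therefore the better fit to the plan.

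**Holm at the final analysis only.** The steps are 0.048/3 = 0.016, 0.048/2 = 0.024 and 0.048/1 = 0.048. Let m be the number of truly ineffective devices. A false rejection occurs in one of two ways:

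- an ineffective device crosses at the interim, with probability at most m x 0.0006; or
- the first false rejection comes at the final analysis. Everything rejected before it is then truly effective, so the step in force is at most 0.048/m, and the probability over m devices is at most 0.048.

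The bound is m x 0.0006 + 0.048, which is 0.0498, 0.0492 and 0.0486 for m = 3, 2 and 1. It does not depend on the correlation through the shared control, on the information fraction, or on whether a crossing ends the trial. The first step is still 0.016, so every rejection under the current rule is kept.

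**Power by simulation.** At least 1,000,000 trials per scenario were run with normal arm means, a shared control and 50 evaluable per arm. Where one crossing ends the trial, the other devices are judged at 0.0006 on the interim data. The table gives the current rule, then Holm.

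| True effects | SD | After a crossing | Each working device | Each ineffective device |
|---|---|---|---|---|
| 10/10/10 | 11.8 | arms continue | 96.6% to 98.5% | – |
| 10/10/10 | 11.8 | trial ends | 73.3% to 74.8% | – |
| 10/10/10 | 16.7 | arms continue | 72.2% to 79.5% | – |
| 10/10/10 | 16.7 | trial ends | 62.6% to 69.0% | – |
| 10/10/0 | 11.8 | arms continue | 96.6% to 97.5% | 1.6% to 4.5% |
| 10/10/0 | 11.8 | trial ends | 81.9% to 82.7% | 0.9% to 2.2% |
| 10/10/0 | 16.7 | arms continue | 72.2% to 75.2% | 1.6% to 3.5% |
| 10/0/0 | 11.8 | arms continue | gain about 0.1 point | 1.6% to 2.5% |

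When all three work, the chance of at least one success is the same under both rules: 99.7% at SD 11.8 and 91.2% at SD 16.7. No rejection made by the current rule was lost in any run.

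**Where the larger steps must not be used.** If a crossing ended the trial and 0.024 and 0.048 were then applied to the interim data, the bound above would no longer hold. With effects 12/12/0, simulated family-wise error was 0.044 with half the information in, 0.049 with 30% and 0.053 with 20%.

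**Intervals.** Every success that Holm adds at the final analysis has a p-value between 0.016 and 0.048. The interval matching 0.016 has level 1 − 0.016 = 98.4% and includes zero for each such device.

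**The case against.** The strongest case against is that this is a preference. The plan names its method, gives the reason for it and controls family-wise error. With three vendors' products, a fixed threshold has real merits: each verdict stands alone, and the matching confidence intervals are simple. The cost is not trivial either. At SD 11.8, with two working devices and arms continuing, each working device gains 0.9 point while the ineffective one's error rises by 4.5 − 1.6 = 2.9 points. The larger gains need all three products to work, and those of 6 to 7 points also need the assumed SD of 16.7. The unstated consequence of a crossing matters far more: at SD 11.8 with all three working, power under the current rule is 73.3% on one reading and 96.6% on the other.

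Most of that stands, and it is why the change is optional. What remains is that Holm rejects everything the current rule rejects, and sometimes more, under the same family-wise bound and without extra patients.

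A reader might infer that the 0.016 threshold is wrong or that the trial fails to control error. The documents do not support that, since the plan's own thresholds sum to 0.0498. A reader might also infer that Holm makes the trial more likely to find an effective product at all. It does not, because its first step is the plan's own threshold.

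**Conclusion.** The current rule is valid, and Holm at the final analysis is a cheap improvement on it. At the plan's SD with all three devices effective, the gain per device is 1.9 points if arms continue and 1.5 points if one crossing ends the trial. At SD 16.7 it is 7.3 and 6.4 points. It shrinks to 0.9 or 0.8 point at SD 11.8 when two devices work, and to about 0.1 point when one does. In return, an ineffective device's own false-positive rate rises, within the family-wise limit.

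The error bound rests on valid p-values, on both thresholds applying to each comparison, and on a family-wise 0.05 that is inferred and not stated. The power figures also rest on two-sided tests, 50 evaluable patients per arm and half the information at the interim. That last fraction is uncertain, because 50% enrollment is not the same as 50% of day-90 outcomes.

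**What to change.** Replace the sentence on the final threshold with wording such as:

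> At the interim each device is tested against control at 0.0006, and a device that crosses counts as rejected. At the final analysis the p-values of the remaining devices are ordered and tested at 0.016, 0.024 and 0.048, starting one step later for each device already rejected and stopping at the first non-rejection.

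Also:

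- State the family-wise level and sidedness (0.05 two-sided, if that is what 0.017 stands for).
- State whether a crossing ends the trial or only that comparison. If it ends the trial, judge the other devices at 0.0006 on the interim data and do not apply 0.024 or 0.048 there.
- Either report intervals compatible with the Holm decisions, or state that the Holm test decides and that the 98.4% interval is conservative and may include zero for a device rejected only at 0.024 or 0.048.
- Adopt the rule before any unblinded comparison.

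The cost is a few sentences and no patients. The plan should acknowledge three downsides: an ineffective device's own error rises when others work, one product's verdict comes to depend on the others' results, and intervals become less simple.

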If you attend one of Yale's Congestive Heart Failure Clinics and are between the ages of 18 and 79, you may be eligible to participate in a free and confidential research study investigating the use of digital health technologies in the care of patients with heart failure. If you enroll, you will potentially receive free access to new digital health tools at no cost to you, and you will be compensated up to \$180 for your time and participation. To learn more or to see if you are eligible to participate, click on "I am interested" or call the Yale Heart Failure Digital Health Study line at [contact]. You can also visit our website at yale.digitalhealthstudy.org for more information.

No action by you is required. You may ignore this message or click "not interested." Thank you very much for considering being a part of research at Yale.

To learn about future research opportunities, you may also create a volunteer profile through the Research Tab in MyChart.

To opt-out of all future research communications, please call the Yale Clinical Trials Office at [name] and select #3.

During an enrollment phone call, the coordinator will discuss the study and instruct the patient through the enrollment process outlined above. The patient will access our study website through a link that will be sent to them via email, text messaging, or other electronic means acceptable to the potential enrollee.

[figure not shown]
Once a patient has electronically consented and created a study profile, an email will be sent with next steps, and will also contain an electronic copy of the signed consent form. They will be directed to complete the KCCQ questionnaire and a medication adherence survey for baseline data collection towards our primary and secondary outcomes, as well as a health literacy assessment and a technology literacy assessment to track any improvements over the course of the study.

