 - Both a health and technology literacy survey, to gauge baseline status that will be tracked throughout the course of the study
 - A KCCQ questionnaire to assess baseline quality of life metrics that will be tracked throughout the course of the study as a measure of primary outcome
 - A medication adherence survey to assess and baseline medication adherence that will be tracked throughout the course of the study
- Patients will be randomized to one of four study arms. Those in one of the three intervention arms will receive the appropriate digital health product. A study coordinator will educate the patient on the product, demonstrating all available features and ensuring the patient understands how to use the product and its value. The digital health product will be mailed to the patient's home and the patient will be encouraged (but not required) to engage with it on a daily basis.

Days 1-89

- Ongoing data collection regarding usage statistics of all digital health products will occur.
- Patients (regardless of randomization status to intervention or usual care groups) will be seen once every
 2-3 weeks at in-person clinic visits as they normally would outside of this study. Physicians will have an opportunity to engage with patients about that data collected from their digital health product and make any changes or recommendations to their plan of care.

Day 90

[figure not shown]
- Patients will have their final in-person clinic visit. At this time, patients will meet with an on-site or virtual (via phone calls) study coordinator and be asked to complete a variety of study-related questionnaires and surveys electronically, including:
 - A health and technology literacy survey, to track progress over the course of the study
 - A KCCQ questionnaire to track any changes over the course of the study as a measure of the primary outcome
 - A medication adherence survey to track changes from baseline
 - A product satisfaction survey (intervention groups only), to determine a Net Promoter Score (NPS) that measures satisfaction with the digital health product
 - A usability survey (intervention groups only), which assesses user friendliness, frequency of use, product satisfaction, and perceived impact of the product.
- Patients will graduate from the clinic, but will be asked to continue using their products until study closeout.

Days 90-179

- Ongoing data collection regarding usage statistics of all digital health products will continue.

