- Patients will receive monthly calls from the clinic, regardless of randomization status, to track progress, assess engagement with products, and answer any questions.

Day 180

- Patients will be asked to complete a final electronic visit with study coordinators for study close-out. They will also be mailed a return-labeled envelope to return the digital health product. During this visit, patients will work with study coordinators and be asked to fill out final assessments electronically, including:
 - A health and technology literacy survey, to track progress over the course of the study
 - A KCCQ questionnaire to track any changes over the course of the study as a measure of the primary outcome
 - o A medication adherence survey to track changes from baseline
 - A product satisfaction survey (intervention groups only), to determine a Net Promoter Score (NPS) that measures satisfaction with the digital health product
 - A usability survey (intervention groups only), which assesses user friendliness, frequency of use, product satisfaction, and perceived impact of the product.
- Study coordinators will collect any final data needed and answer any remaining questions, and patients will complete their participation in the study.

The study timeline for an enrolled patient is as follows:

Clinician Data Collection

An important aspect of our study is to determine whether the digital health products enhance clinical efficiency and reduces physician burden. At the end of the study, we will ask participating clinicians to complete an anonymous survey that assesses physician satisfaction with the products, ease of use, effect on workload and efficiency, and contribution to clinical-decision making.

Outcomes

Our primary outcome is the rate of improved quality of life of enrolled patients after 90 days as measured by the Kansas City Cardiomyopathy Questionnaire (KCCQ), which will be given to patients prior to enrollment, at the 90 day mark, and after study completion (day 180). The KCCQ is a standardized 23- question instrument that combines aspects of physical functions, symptoms (frequency, severity, and recent changes), social function, self-efficacy, and quality of life into a single summary score on a scale of 0 to 100, giving a sensitive and specific measure of quality of life for heart failure patients.

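### The primary-model sentence names neither baseline KCCQ nor clinic; stating one model that adjusts for both, before the interim analysis, is a minor improvement at almost no cost

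*Combined protocol and SAP*

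**What the plan says.** All references are to the combined protocol and SAP.

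- **Primary model.** Section I, item 13 (Statistical Considerations) specifies a "mixed effects model comparing change in KCCQ over time in the intervention group versus the control, without accounting for a center-by-treatment interaction". Centre appears only through the interaction that is left out, which is taken up in secondary analyses. The random effects are not listed.
- **Baseline KCCQ.** It is part of the Day 0 assessments for all consented patients: "A KCCQ questionnaire to assess baseline quality of life metrics". Subject Eligibility and Recruitment says the same: "They will be directed to complete the KCCQ questionnaire and a medication adherence survey for baseline data collection". The Outcomes section describes the KCCQ as an instrument "which will be given to patients prior to enrollment, at the 90 day mark, and after study completion (day 180").
- **Clinic.** Subject Randomization and Intervention stratifies the randomisation lists by clinic. Item 13 also stratifies the baseline comparisons by clinic site.
- **Sample size.** Item 13 cites a "within-patient standard of deviation of 11.8 for patients with no change in clinical status" and concludes that "we would need to enroll 40 patients in each arm of the trial across all centers to provide 90% power" at alpha 0.017. It then raises the target to 50 per arm: "Given uncertainties around the intraclass correlation coefficient (assumed to be 0.10 here and reflecting the overall efficacy of each individual clinic"). The final significance threshold is 0.016.
- **Endpoint wording.** Outcomes states: "Our primary outcome is the rate of improved quality of life of enrolled patients after 90 days". Item 13 analyses change in score.

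**The concern.** The plan collects a strong predictor of the outcome and stratifies on clinic, yet its model sentence uses neither. Two consequences are possible.

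- **Baseline.** A change contrast with arm means left free at baseline fixes the baseline coefficient at one. Estimating the coefficient, or constraining the arms to a common baseline mean, extracts at least as much information from the same patients in large samples.
- **Clinic.** With individual randomisation stratified by clinic, between-clinic variation cancels out of the treatment contrast. If clinic is not in the model, that variation stays in the residual. The reported standard error is then larger than the true one and the test is conservative.

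Several models with different standard errors fit the sentence as it stands. The trial is unblinded and has an interim efficacy look at p < 0.0006, so it is better to settle on one model before outcome data are examined.

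**Working it through.** **Inputs from item 13.** Difference 10 points; SD 11.8; alpha 0.017 for design and 0.016 at the end; 90% power; 40 then 50 per arm; clinic ICC 0.10; 5 patients per arm per clinic.

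**Assumed, not in the documents.** Two-sided testing; 11.8 read as the SD of change; total (baseline) SD 18 to 25; day-90 SD equal to the baseline SD or 10% above or below it.

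**1. The plan's own figure.** The normal approximation n = 2(11.8/10)²(z₀.₉₉₁₅ + z₀.₉₀)² gives 38 per arm. The noncentral t needs 39 (power 0.9006), and 40 gives 0.909. The stated 40 therefore reproduces with 11.8 as the SD of change. A one-sided test would need 33 and does not match. At 50 per arm and alpha 0.016, unadjusted power is 0.961.

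**2. Baseline.** Let s0 and s1 be the SDs at baseline and day 90, and ρ their correlation.

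- Variance of change: s0² + s1² − 2ρ·s0·s1
- Variance after adjustment: s1²(1 − ρ²)
- Difference: (s0 − ρ·s1)², which is never negative

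Holding the SD of change at 11.8 gives ρ = (s0² + s1² − 11.8²)/(2·s0·s1). Example with s0 = s1 = 20: ρ = (800 − 139.24)/800 = 0.826. The variance falls by (20 − 0.826×20)² ≈ 12.1 out of 139.24, or 8.7%.

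| Day-90 SD | ρ (s0 = 18 to 25) | Variance reduction | Power, 50 per arm, alpha 0.016 |
|---|---|---|---|
| Equal to s0 | 0.785 to 0.889 | 10.7% to 5.6% | 0.978 to 0.970 |
| 1.1 × s0 | 0.809 to 0.903 | 2.8% to 0.0% | 0.966 to 0.961 |
| 0.9 × s0 | 0.767 to 0.882 | 22.3% to 19.1% | 0.990 to 0.987 |

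**3. Clinic.** In large samples, reported variance without clinic divided by true variance is 1/(1 − ICC). At ICC 0.10 the SE ratio is 1/√0.90 = 1.054. With few clinics the excess is a little smaller. I simulated 6 and 9 clinics, as the rollout and Subject Population sections suggest, and 10, which is 50 per arm divided by 5 per clinic. Each setting had 100,000 null trials, balanced arms, total SD 1, and clinic as a fixed effect when included.

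| Clinics × patients per arm | Empirical SE | Reported SE without / with clinic | Type I error at 0.016 without / with |
|---|---|---|---|
| 6 × 8 | 0.1942 | 0.2021 / 0.1932 | 0.0122 / 0.0159 |
| 6 × 5 | 0.2451 | 0.2553 / 0.2439 | 0.0121 / 0.0160 |
| 9 × 5 | 0.1998 | 0.2092 / 0.1994 | 0.0115 / 0.0159 |
| 10 × 5 | 0.1907 | 0.1987 / 0.1892 | 0.0120 / 0.0162 |

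Without clinic the reported SE is 4.0-4.7% above the empirical SE.

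**4. How clinic must enter.** Step 3 concerns a single analysed outcome. If baseline is instead kept as an outcome row with a common baseline mean, and the ICC of 0.10 applies to change, a clinic effect constant over visits does not do the job. One simulation (10 clinics × 5 per arm, four arms, baseline SD 20, 1,500 runs) gave mean reported SEs of 2.254 without clinic, 2.236 with a clinic main effect and 2.139 with clinic-by-visit. The main effect recovers 0.018/0.115 = 16% of the excess. A second simulation gave 2.242, 2.244 and 2.126, so nothing was recovered. In a day-90 analysis with baseline as a covariate, a clinic main effect is enough (2.261 to 2.146).

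**The case against.** **Clinic may already be intended.** The plan calls the model mixed effects, assumes a clinic ICC, and excludes only the interaction, which suggests that a clinic main or random effect is present. A common-baseline-mean model would also fit the sentence. This stands: both losses are possible, not established. But a model with only a patient random effect fits the sentence equally well, and the text does not decide between them.

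**Adjustment need not help.** The variance inequality is a large-sample result. The lost degree of freedom costs about 0.5% of the SE at 50 per arm, and one corner of the grid shows no gain. A reader might infer that naming baseline can only help; the accurate statement is that it helps or is close to neutral.

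**Power is already ample.** This is true only if 11.8 is the SD of change. The plan calls it within-patient. If it is the SD of a single measurement, the SD of change is 11.8×√2 = 16.7, unadjusted power at 50 per arm is about 71%, and adjusted power is 72-88% over the same grid. The 11.8 also comes from clinically unchanged patients, so the variability in this trial may differ.

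**Stronger readings.** A reader might infer that leaving clinic out makes the SE too small, as in a cluster-randomised trial, or that the primary result would be biased. The documents support neither: patients are randomised individually within clinic, so the effect of omission is conservative, and the change contrast is unbiased.

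**Conclusion.** The point holds as a minor matter of efficiency and pre-specification. The primary-model sentence leaves out two terms that the design makes available.

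- **Baseline adjustment** would reduce the variance by about 0-22%, worth 0-3 points of power at 50 per arm. This rests on a change SD of 11.8, total SD 18-25, and a day-90 SD within 10% of baseline.
- **Clinic** does not make the estimate itself more precise in a balanced design. Including it removes a 4-5% overstatement of the reported SE and brings the actual level from about 0.012 to about 0.016. This rests on the ICC of 0.10 applying to the analysed change and on no clinic effect being fitted already.

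Neither the type I error rate nor the validity of the estimate is in question. All of this concerns the continuous KCCQ score. If the primary endpoint is a responder rate, these figures do not carry over.

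**What to change.** First reconcile the Outcomes section with item 13: is the primary endpoint the continuous day-90 KCCQ score or a rate of improvement? If it is the continuous score, replace the model sentence in item 13 before the interim analysis with one model, for example:

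> Post-baseline KCCQ (day 90 and day 180) will be analysed in a mixed model for repeated measures with treatment, visit, treatment-by-visit, baseline KCCQ, baseline-by-visit, clinic and clinic-by-visit. The primary contrast is each device versus control at day 90.

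State whether clinic is fixed (the form simulated above) or random, and name the within-patient covariance structure. If the investigators prefer to keep baseline as an outcome with a common baseline mean, clinic must enter as clinic-by-visit. Keep treatment-by-clinic as the secondary analysis.

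The cost is two or three sentences and the investigators' confirmation of the endpoint. No new data, visits or patients are needed.
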